# 7.5 Safety Set

# Solicited Safety Set (solicited local and systemic adverse events and other solicited adverse events)

All subjects in the Exposed Set with any solicited adverse event data and/or indicators of solicited adverse events.

# **Unsolicited Safety Set (unsolicited adverse events)**

All subjects in the Exposed Set with unsolicited adverse event data.

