# 7.2 Exposed Set

All subjects in the All Enrolled Set who receive a study vaccination.

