# 7.7 Overview of Analysis Sets by PD Code

Table 7.7-1: Safety Sets

PD code	PD Description	Study Objective/ Period	All Exposed Set	Overall Safety Set	Safety Set, Solicited AEs, Period 1, T6H-D7	Safety Set, Solicited AEs, Period 2, T6H-D7	Unsolicited Safety set
	Exclusion code		EXPFL	SAFFL	SSS10FL	SSS11FL	SSU10FL
100	Study vaccine not administered AT ALL	All Study	EXC	EXC	EXC	EXC	EXC
115	Subject did not provide any post-vaccination unsolicited safety data	All Study					EXC
116.1	Subject did not provide any post-vaccination solicited safety data after vaccination 1	All Study (follow on)/First vaccination (Naive)			EXC		
116.2	Subject did not provide any post-vaccination solicited safety data after vaccination 2*	Second vaccination				EXC	

EXC = excluded from this analysis set.

\*applicable to naive subjects only.

PD code	PD Description	Study objective/ period	FAS IMM Persistence (Day 1)	FAS IMM (Day 31)	FAS IMM (Days 6, 31/Days 66, 91)	PPS IMM Persistence (Day 1)	PPS IMM (Day 31)	PPS IMM (Days 6, 31/Days 66, 91)
	Exclusion code		FAS10FL	FAS11FL	FAS12FL	PPS10FL	PPS11FL	PPS12FL
100	Study vaccine not administered AT ALL	Day 1 – End of study		EXC	EXC		EXC	EXC
110. 100	Serological results (A, C, W, Y and 4 B strains) are not available  Visit not done, blood draw not done	Day 1	EXC		EXC	EXC		EXC
110.d.102	Serology results are not available  Serological results (A, C, W, Y and 4 B strains) are not available	Day 1	EXC		EXC	EXC		EXC
110. 200	Serological results (A, C, W, Y and 4 B strains) are not available  Visit not done, blood draw not done	Day 6 (follow on) Day 66 (naive)			EXC			EXC
110.d.202	Serology results are not available  Serological results (A, C, W, Y and 4 B strains) are not available	Day 6 (follow on) Day 66 (naive)			EXC			EXC

	lential	

PD code	PD Description	Study objective/ period	FAS IMM Persistence (Day 1)	FAS IMM (Day 31)	FAS IMM (Days 6, 31/Days 66, 91)	PPS IMM Persistence (Day 1)	PPS IMM (Day 31)	PPS IMM (Days 6, 31/Days 66, 91)
110. 300	Serological results (A, C, W, Y and 4 B strains) are not available  Visit not done, blood draw not done	Day 31		EXC	EXC (follow on only)		EXC	EXC (follow on only)
110.d.302	Serology results are not available  Serological results (A, C, W, Y and 4 B strains) are not available	Day 31		EXC	EXC (follow on only)		EXC	EXC (follow on only)
110. 500	Serological results (A, C, W, Y and 4 B strains) are not available  Visit not done, blood draw not done	Day 91			EXC (naive only)			EXC (naive only)

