#### 13.1.1 Safety Completeness Analysis

#### Solicited adverse events

The safety completeness analysis on solicited adverse events aims to identify subjects who completed diary cards, irrespective of severity. The analysis will show the number of subjects with *valid data* by solicited adverse event and time point. *Valid data* in the context of the safety completeness analysis are all data entered in the diary card (including implausible values) except "Not done/unknown".

Four summaries will be produced:

- 1. The frequencies of subjects who provide diary cards by vaccine group.
- 2. For each solicited adverse event, the frequencies of subjects with *valid data* will be presented by vaccine group and timepoint: 30 min, 6h, days 2, 3, 4, 5, 6 and 7.
- 3. For each type of solicited adverse event (local, systemic) and indicators of solicited adverse events, such as analgesic use the frequencies of subjects *with valid data* by vaccine group, aggregated over time points: 6h day 7.

4. For each solicited adverse event, the frequencies of subjects *with valid data* by vaccine group, aggregated over time points: 6h - day 7.

For the corresponding percentages, the denominator will be the respective numbers of exposed subjects, i.e., subjects who received a vaccination and were still in-study for that time point or time interval, irrespective of whether a ediary card was present or not.

All analyses will be based on the 'as treated' analysis set.

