For each of the time points or time intervals presented in the summaries, only subjects with at least one plausible observation (i.e., any non-missing values but excluding "Not done/unknown" and implausible values) for the solicited adverse events in the interval of interest will be considered. Subjects without plausible data (i.e. missing values or reported as "Not done/unknown" and implausible values) will be removed from the denominator to prevent a downward bias (towards zero).

The analysis of solicited AE after first vaccination (applicable to all vaccine groups) will be reported separated from the analyses of solicited AE after second vaccination and after any vaccination (applicable only to naive subjects).

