#### 13.3 Unsolicited Adverse Events

All the unsolicited adverse events occurring during the study, judged either as probably related, possibly related, or not related to vaccination by the investigator, will be recorded. The original verbatim terms used by investigators to identify adverse events in the CRFs will be mapped to preferred terms using the MedDRA dictionary. The unsolicited adverse events will then be grouped by MedDRA preferred terms into frequency tables according to system organ class. Adverse events judged by the investigator as at least possibly related to study vaccine will be summarized by vaccine group, according to system organ class and preferred term within system organ class. When an unsolicited adverse event occurs more than once for a subject, the maximal severity and strongest relationship to the vaccine group will be counted.

Only vaccine-emergent adverse events (see section 8.7 for definition) will be analyzed, i.e., excluding those after a subject has given informed consent but before vaccination. The selection of unsolicited adverse events and the assignment to time intervals will be done by day of onset and not by days ongoing/persisting.

The analysis of unsolicited adverse events comprises the following categories:

- Any unsolicited adverse event (from day 1 to day 31 all vaccine groups, from day 61 to day 91 and after any vaccination (day 1-31 and day 61-91) for naive groups only)
- Possibly or probably related unsolicited adverse events (from day 1 to day 31 all vaccine groups, from day 61 to day 91 and after any vaccination (day 1-31 and day 61-91) for naive groups only)
- Unsolicited adverse events leading to death (from day 1 to end of study for all vaccine groups).

- Serious adverse events (from day 1 to end of study for all vaccine groups).
- Possibly or probably related serious adverse event (from day 1 to end of study for all vaccine groups).
- Unsolicited adverse events leading to premature withdrawal from study (from day 1 to end of study for all vaccine groups).
- Unsolicited adverse events leading to dose reduction, interruption or delay in study vaccination (from day 1 to end of study for all vaccine groups).
- Medically attended adverse events (from day 1 to end of study for all vaccine groups).

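### The Day 61–91 unsolicited AE tables for naive subjects have no dose-2 denominator, so on the sets as defined they do not estimate the post-dose-2 rate

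*SAP*

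**What the plan says.** The Unsolicited Safety Set in SAP 7.5 carries no dose or period condition: "All subjects in the Exposed Set with unsolicited adverse event data". Protocol 8.3.3 has the same definition, and Protocol 8.4.3.3.5 names no period version. The Exposed Set on which it rests (SAP 7.2) needs only one dose: "All subjects in the All Enrolled Set who receive a study vaccination".

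Table 7.7-1 in SAP 7.7 gives the set one flag, SSU10FL. Two codes remove a subject from it: code 100 (never vaccinated) and code 115, "Subject did not provide any post-vaccination unsolicited safety data", whose period is the whole study.

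SAP 13.3 reports any unsolicited AE, and related unsolicited AEs, for Day 1–31 in all groups and then "from day 61 to day 91 and after any vaccination (day 1-31 and day 61-91) for naive groups only". Events are placed in intervals by onset day. No denominator is stated for Day 61–91.

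Solicited AEs are handled differently. Table 7.7-1 has a "Safety Set, Solicited AEs, Period 2, T6H-D7" (flag SSS11FL) with its own exclusion code, 116.2. SAP 13.2 adds that subjects without plausible data in the interval "will be removed from the denominator to prevent a downward bias (towards zero"). The solicited completeness analysis in SAP 13.1.1 uses as its denominator "subjects who received a vaccination and were still in-study for that time point or time interval".

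**The concern.** A percentage headed Day 61–91 in the naive groups will be read as the AE rate after the second dose. If the denominator includes subjects who never had that dose, it is a mixture of two rates. Secondary safety objective 3 is the safety and reactogenicity of two doses in naive subjects, and readers will naturally set the Day 61–91 column beside the Day 1–31 column. Two doses with the same true rate could then appear to differ because of the denominator alone.

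The plan recognises this problem for solicited AEs and corrects for it. SAP 8.2 also says that safety is analysed by interval in order to limit the effect of dropouts. An interval split does not do that if the same set is the denominator in every interval.

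**Working it through.** The documents give no unsolicited AE rate, no dose-2 dropout rate and no precision figure for this analysis, so there is no planned figure to reproduce. The check has two steps.

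**Step 1: does a subject without dose 2 stay in the set?** Take a naive subject who received dose 1, gave unsolicited data and did not receive dose 2.

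- Exposed Set (SAP 7.2): met, since one vaccination is enough.
- Unsolicited Safety Set (SAP 7.5): met, since unsolicited data exist.
- Code 100: does not apply, because the subject was vaccinated.
- Code 115: does not apply, because some unsolicited data were provided during the study.

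No rule removes this subject, and SSU10FL is the only unsolicited set available for the Day 61–91 tables.

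**Step 2: what does that do to the percentage?** Let

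- d = share of the naive set without dose 2,
- p = Day 61–91 rate among dose-2 recipients,
- b = rate counted in that window among subjects without dose 2.

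Then

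reported rate = (1−d)·p + d·b, and understatement = p − reported = d·(p − b).

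Subjects who left before dose 2 have b = 0. Subjects denied dose 2 may stay in the study (Protocol 4.3), and an AE with onset in the window can then be counted. SAP 8.8 would tie such an AE to the most recent vaccination, which is dose 1, so it is not a post-dose-2 event.

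All values of d, p and b below are assumptions:

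| d | p = 10%, b = 0 | p = 30%, b = 0 | p = 30%, b = p/2 = 15% |
|---|---|---|---|
| 2% | 9.8% | 29.4% | 29.7% |
| 5% | 9.5% | 28.5% | 29.25% |
| 10% | 9.0% | 27.0% | 28.5% |
| 20% | 8.0% | 24.0% | 27.0% |

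Worked example: d = 5%, p = 30%, b = 0 gives 0.95 × 30% = 28.5%, which is 1.5 points low. With b = 15% it is 28.5% + 0.05 × 15% = 29.25%, which is 0.75 points low. At b = p the understatement is zero for every d.

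With the denominator restricted to dose-2 recipients, d = 0 and the reported rate equals p.

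For scale, each naive group has about 100 subjects (200 randomised 1:1), so d = 5% is about five subjects per group. The approximate 95% half-width for a 30% rate is 1.96 × √(0.3 × 0.7/100) ≈ 9 points.

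**The case against.** The strongest reply is that the denominator is inferred. SAP 13.3 does not state it. The table list, mock-ups and program specifications are held outside these documents. The list of unsolicited intervals announced in SAP 8.2.1 is blank in the text available, which may be an extraction loss and is not held against the plan. SAP 6.1 writes the code as 115.x, which suggests that sub-codes were foreseen. SAP 8.2.1 also includes an imputation provision for unsolicited AEs.

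Part of this stands. The documents do not prove that the tables will be programmed this way. But nothing in them overrides the set as defined: Table 7.7-1 carries only a whole-study code 115, and the missing-data trigger in SAP 8.2.1 is worded for absent solicited data.

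The reply on size also stands. The two unknowns are assumed, the shift at low dropout is well inside sampling error, safety has no hypotheses (Protocol 8.4.3.3.4) and no success criteria (Protocol 8.2.2.3), and withdrawals and vaccinations received are tabulated (SAP 9.1, 13.1).

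A reader might infer two stronger points, and neither is supported:

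- **That nobody without dose 2 can have an AE counted in the window.** This is true only of those who left. Protocol 4.3 encourages subjects barred from further doses to continue, Protocol 3.8.6 does the same for pregnancy, and AEs are assigned by onset day. Multiplying the true rate by (1−d) is therefore the worst case and not a general formula.
- **That a dose-2 set would remove selection.** Dose-2 recipients exclude subjects stopped for reactions to dose 1, whichever denominator is used. The change corrects dilution and leaves that selection in place.

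**Conclusion.** The point holds in a limited form. With one whole-study unsolicited set and no other stated denominator, the Day 61–91 percentages in the naive groups mix dose-2 recipients with subjects who never had dose 2, and so do not estimate the post-dose-2 rate. The understatement is d·(p − b). At an assumed p of 30% it is at most 1.5 points for d = 5% and 3.0 points for d = 10%, reached when b = 0. It is half that at b = p/2 and nil at b = p.

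The conclusion rests on the tables using the set that the SAP defines, and the size rests on values that the documents do not give. Follow-on groups, Day 1–31 tables, whole-study SAE and withdrawal tables, and all immunogenicity results are unaffected. It merits correction because the plan already applies the remedy to solicited AEs and the change is small.

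**What to change.** In SAP 7.5 and Table 7.7-1, add a Period 2 Unsolicited Safety Set (for example SSU11FL, with code 115.2, parallel to SSS11FL and 116.2). It would contain naive subjects who received dose 2 and have unsolicited safety data after it. Subjects who withdraw after receiving dose 2 should stay in, since they were exposed.

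Name this set in SAP 13.3 as the denominator for the Day 61–91 tables of any unsolicited AE and of related unsolicited AEs. Leave the Day 1–31, any-vaccination and whole-study tables on SSU10FL. A footnote giving the number of naive subjects in SSU10FL without dose 2 would let readers see d directly.

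The cost is one extra flag and exclusion code, a changed denominator in the naive Day 61–91 tables, and probably slightly less favourable post-dose-2 percentages.

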# **Overall Safety Set**

All subjects who are in the Solicited Safety Set and/or Unsolicited Safety Set.

In case of vaccination error, subjects will be analyzed as "treated" (i.e., according to the vaccine a subject receives, rather than the vaccine to which the subject is randomized).

If a subject received the correct study vaccine (dose, batch) but from another ongoing study at the site then the subject's safety data should be included in the safety analysis.

## 7.5.1 Restricted Safety Set

Not applicable.

# 7.6 Other Analysis Set

Not applicable.

# 7.7 Overview of Analysis Sets by PD Code

Table 7.7-1: Safety Sets

PD code	PD Description	Study Objective/ Period	All Exposed Set	Overall Safety Set	Safety Set, Solicited AEs, Period 1, T6H-D7	Safety Set, Solicited AEs, Period 2, T6H-D7	Unsolicited Safety set
	Exclusion code		EXPFL	SAFFL	SSS10FL	SSS11FL	SSU10FL
100	Study vaccine not administered AT ALL	All Study	EXC	EXC	EXC	EXC	EXC
115	Subject did not provide any post-vaccination unsolicited safety data	All Study					EXC
116.1	Subject did not provide any post-vaccination solicited safety data after vaccination 1	All Study (follow on)/First vaccination (Naive)			EXC		
116.2	Subject did not provide any post-vaccination solicited safety data after vaccination 2*	Second vaccination				EXC	

EXC = excluded from this analysis set.

\*applicable to naive subjects only.

PD code	PD Description	Study objective/ period	FAS IMM Persistence (Day 1)	FAS IMM (Day 31)	FAS IMM (Days 6, 31/Days 66, 91)	PPS IMM Persistence (Day 1)	PPS IMM (Day 31)	PPS IMM (Days 6, 31/Days 66, 91)
	Exclusion code		FAS10FL	FAS11FL	FAS12FL	PPS10FL	PPS11FL	PPS12FL
100	Study vaccine not administered AT ALL	Day 1 – End of study		EXC	EXC		EXC	EXC
110. 100	Serological results (A, C, W, Y and 4 B strains) are not available  Visit not done, blood draw not done	Day 1	EXC		EXC	EXC		EXC
110.d.102	Serology results are not available  Serological results (A, C, W, Y and 4 B strains) are not available	Day 1	EXC		EXC	EXC		EXC
110. 200	Serological results (A, C, W, Y and 4 B strains) are not available  Visit not done, blood draw not done	Day 6 (follow on) Day 66 (naive)			EXC			EXC
110.d.202	Serology results are not available  Serological results (A, C, W, Y and 4 B strains) are not available	Day 6 (follow on) Day 66 (naive)			EXC			EXC

	lential	

PD code	PD Description	Study objective/ period	FAS IMM Persistence (Day 1)	FAS IMM (Day 31)	FAS IMM (Days 6, 31/Days 66, 91)	PPS IMM Persistence (Day 1)	PPS IMM (Day 31)	PPS IMM (Days 6, 31/Days 66, 91)
110. 300	Serological results (A, C, W, Y and 4 B strains) are not available  Visit not done, blood draw not done	Day 31		EXC	EXC (follow on only)		EXC	EXC (follow on only)
110.d.302	Serology results are not available  Serological results (A, C, W, Y and 4 B strains) are not available	Day 31		EXC	EXC (follow on only)		EXC	EXC (follow on only)
110. 500	Serological results (A, C, W, Y and 4 B strains) are not available  Visit not done, blood draw not done	Day 91			EXC (naive only)			EXC (naive only)
110.d.502	Serology results are not available Serological results (A, C, W, Y and 4 B strains) are not available	Day 91			EXC (naive only)			EXC (naive only)
112.102	Obvious deviation from Laboratory Manual or error in laboratory data (HT-SBA)	Day 1				EXC		EXC
112.202	Obvious deviation from Laboratory Manual or error in laboratory data (HT-SBA)	Day 6 (follow on) Day 66 (naive)						EXC

PD code	PD Description	Study objective/ period	FAS IMM Persistence (Day 1)	FAS IMM (Day 31)	FAS IMM (Days 6, 31/Days 66,	PPS IMM Persistence (Day 1)	PPS IMM (Day 31)	PPS IMM (Days 6, 31/Days 66,
112.302	Obvious deviation from Laboratory Manual or error in laboratory data (HT-SBA)	Day 31			91)		EXC	EXC (follow on only)
112.502	Obvious deviation from Laboratory Manual or error in laboratory data (HT-SBA)	Day 91						EXC (naive only)
120.100	Randomization failure to treatment	Day 1				EXC (naive only)	EXC (naive only)	EXC (naive only)
140.100	Vaccination not according to protocol	Day 1				EXC	EXC	EXC
140.300	Vaccination not according to protocol	Day 61 (Naive only)						EXC (naive only)
150.100	Administration of forbidden vaccine	Day 1 (before BS_1)				EXC	EXC	EXC
150.300	Administration of forbidden vaccine	Day 1 (after BS_1)- day 7					EXC	EXC
150.500	Administration of forbidden vaccine	-7/+7 2 nd vaccination (naive only)						EXC (naive only)
200	Subject did not meet entry criteria	Day 1 – end of study				EXC	EXC	EXC

PD code	PD Description	Study objective/ period	FAS IMM Persistence (Day 1)	FAS IMM (Day 31)	FAS IMM (Days 6, 31/Days 66, 91)	PPS IMM Persistence (Day 1)	PPS IMM (Day 31)	PPS IMM (Days 6, 31/Days 66, 91)
220	Subject had contraindication for a subsequent study vaccination but was vaccinated	Day 1- Day 61 (naive only)						EXC
230.101	Administration of forbidden medication	Day 1				EXC	EXC	EXC
230.102	Administration of forbidden medication: ANTIBIOTICS	Day 1 (before BS_1)				EXC		
230.201	Administration of forbidden medication	Day 6 (follow on) Day 66 (naive)					EXC (follow on only)	EXC
230.202	Administration of forbidden medication: ANTIBIOTICS	Day 6 (follow on) Day 66 (naive)						EXC
230.301	Administration of forbidden medication	Day 31					EXC	EXC
230.302	Administration of forbidden medication: ANTIBIOTICS	Day 31 (before BS_2)					EXC	EXC (follow on only)
230.501	Administration of forbidden medication	Day 91						EXC (naive only)
230.502	Administration of forbidden medication: ANTIBIOTICS	Day 91						EXC (naive only)
240	Underlying medical condition forbidden by the protocol	Day 1- end of study				EXC	EXC	EXC

$\sim$	~		
Con	†10	en:	tıa.
COL		$\iota\iota\iota\iota\iota$	ши.

PD code	PD Description	Study objective/ period	FAS IMM Persistence (Day 1)	FAS IMM (Day 31)	FAS IMM (Days 6, 31/Days 66, 91)	PPS IMM Persistence (Day 1)	PPS IMM (Day 31)	PPS IMM (Days 6, 31/Days 66, 91)
260.100	Did not comply with study vaccination schedule	Day 1					EXC	EXC
260.200	Did not comply with study vaccination schedule	Day 61 (naive only)						EXC
270.100	Did not comply with blood draw schedule*	Day 1				EXC		EXC
270.200	Did not comply with blood draw schedule	Day 6 (follow on) Day 66 (naive)						EXC
270.300	Did not comply with blood draw schedule*	Day 31					EXC	EXC (follow on only)
270.400	Did not comply with blood draw schedule	Day 91						EXC (naive only)

\*e.g. BD after vaccination

FAS = Full Analysis Set; PPS=Per Protocol Set; EXC = excluded from this analysis set.

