8.4.2.2.2 Analysis Sets

The analysis set to be used for all primary immunogenicity objectives in the Full Analysis Set. Analysis of the objectives will, in any case, be based on both the Full Analysis Set and the Per Protocol Set.

(Amended 4 April 2018)

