# 6. DETERMINATION OF PROTOCOL DEVIATIONS

#### **6.1** Definition of Protocol Deviations

CSR reportable PD are defined in accordance with ICH E3 as important PDs related to study inclusion or exclusion criteria, conduct of the trial, subject management or subject assessment resulting in the potential to jeopardize the safety or rights of the trial subjects or the scientific value of the trial.

All reportable PDs will be evaluated before the analysis and classified according to ICH into the following five categories:

- Subject developed withdrawal criteria during the study but was not withdrawn
- Underlying medical condition forbidden by the protocol or which may influence immune response (PD code 240).
- Subject had contraindication for a subsequent study vaccination but was vaccinated (PD code 220).
- Concomitant infection related to the vaccine which may influence immune response (PD code 250).
- Subject received wrong vaccine or incorrect dose
- Study vaccine was not administered at all (PD code 100)
- Vaccine administration not according to protocol (PD code 140.x).
- Randomization failure (vaccination not according to randomization) (PD code 120).
- Subject took an excluded concomitant medication
- Administration of concomitant vaccine(s) forbidden in the protocol (PD code 150.x).
- Administration of any medication forbidden by the protocol (PD code 230.x).
- Subject randomized and did not satisfy the entry criteria
- Subject did not meet entry criteria (PD code 200).
- Deviation from key study procedures
- Subject did not comply with study vaccination schedule (PD code 140.x).
- Subject did not provide any post-vaccination unsolicited safety data (PD code 115.x).

- Subject did not provide any post-vaccination solicited safety data (PD code 116.x).
- Subject did not comply with blood draw schedule (PD code 270.x).
- Serological results not available post-vaccination (PD code 110.x).
- Obvious incoherence, abnormal serology evolution or error in data (PD code 112).

CSR reportable PDs will lead to exclusion of the subject or part of the subject's data from at least one analysis set.

The number of subjects in any and by PD category will be summarized by vaccine, center and overall. Individual subject listings will be provided in an appendix, sorted by subject and by PD category.

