# 7.3 Full Analysis Set (FAS), Immunogenicity Set

Full Analysis Set Persistence (24 months after last vaccination in V102\_15) – FAS Persistence (Day 1)

All subjects in the All Enrolled Set, who are randomized (if naive), and

• Provide evaluable serum sample with results for at least one serogroup B test strain or serogroups A, C, W or Y at Day 1 in the extension study.

Full Analysis Set Immunogenicity (Day 31, after booster dose [follow-on]/first dose [naive]) – FAS Immunogenicity (Day 31)

All subjects in the All Enrolled Set, who are randomized (if naive), and:

- Receive at least one study vaccination and,
- Provide evaluable serum sample with results for at least one serogroup B test strain or serogroups A, C, W or Y (only after MenABCWY vaccination) at Day 31 in the extension study.

Full Analysis Set Immunogenicity (Days 6 and 31, after booster dose [follow-on]/ Days 66 and 91 after second dose [naive]) – FAS Immunogenicity (Days 6, 31/Days 66, 91)

All subjects in the All Enrolled Set, who are randomized (if naive), and:

- Receive at least one study vaccination and,
- Provide evaluable serum sample with results for at least one serogroup B test strain or serogroups A, C, W or Y (only after MenABCWY vaccination) at Day 1,

and in addition at least at Day 6 or Day 31 (follow-on subjects) / Day 66 or Day 91 (naive subjects) in the extension study.

In case of vaccination error, subjects in the FAS sets will be analyzed "as randomized" (i.e., according to the vaccine a subject was designated to receive, which may be different from the vaccine the subject actually received).

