# 8.2.2 Immunogenicity Data

Missing immunogenicity values are considered MCAR and therefore will not contain information that impact the result of the analysis (i.e., not informative). Imputation methods will therefore not be used. The primary objectives will be analyzed using both the FAS and the PPS.

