## Analysis Sets

The analysis set to be used for all secondary immunogenicity objectives is the Full Analysis Set. Analysis of the objectives will, in any case, be based on both the Full Analysis Set and the Per Protocol Set.

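### As written, HT-hSBA titres confirmed as laboratory errors (code 112.x) stay in the Full Analysis Set, and a wrong Day 1 titre stays as baseline in the Day 31 per-protocol set

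*SAP*

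**What the plan says.** SAP section 7.7 assigns deviation codes to three FAS columns and three PPS columns. Code 112.x has four rows (Day 1, Day 6/66, Day 31, Day 91), each labelled "Obvious deviation from Laboratory Manual or error in laboratory data (HT-SBA". SAP section 6.1 describes the same code differently: "Obvious incoherence, abnormal serology evolution or error in data (PD code 112". The table's key reads "EXC = excluded from this analysis set", and section 6.1 adds that "CSR reportable PDs will lead to exclusion of the subject or part of the subject's data from at least one analysis set".

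Protocol 8.4.2.2.2 names the set for the primary objective: "The analysis set to be used for all primary immunogenicity objectives in the Full Analysis Set" (the second 'in' evidently stands for 'is'). SAP section 11.3 says "The analysis set to be used for all secondary immunogenicity objectives is the Full Analysis Set", as does Protocol 8.4.3.2.2. The PPS is run alongside; SAP 8.2.2 states that "The primary objectives will be analyzed using both the FAS and the PPS".

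To enter FAS Persistence under SAP 7.3 a subject must "Provide evaluable serum sample with results for at least one serogroup B test strain or serogroups A, C, W or Y at Day 1". Neither document defines *evaluable*.

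**The concern.** A full analysis set keeps subjects despite deviations in conduct. An assay result confirmed as wrong is a different matter: it is an invalid measurement, and nothing is gained by analysing it. The SAP recognises this for safety data, where section 6.3 removes implausible measurements from the analysis and lists them. It has no counterpart for titres, which carry the primary endpoint.

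At stake are the Day 1 GMTs and percentages at or above LLOQ in the named analysis set. A Day 1 titre is also the denominator of that subject's GMRs and the reference for each four-fold rise, so one wrong value passes into several secondary endpoints.

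**Working it through.** **Step 1: read the table.** Row 110.100 (no Day 1 blood draw) is included to confirm the column alignment. A fragment of a wrapped column header appears in the FAS part of row 112.302; it is not an exclusion.

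| Code (visit) | FAS Persistence | FAS Day 31 | FAS Days 6,31/66,91 | PPS Persistence | PPS Day 31 | PPS Days 6,31/66,91 |
|---|---|---|---|---|---|---|
| 110.100 (Day 1) | EXC | – | EXC | EXC | – | EXC |
| 112.102 (Day 1) | – | – | – | EXC | – | EXC |
| 112.202 (Day 6/66) | – | – | – | – | – | EXC |
| 112.302 (Day 31) | – | – | – | – | EXC | EXC, follow-on |
| 112.502 (Day 91) | – | – | – | – | – | EXC, naive |

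No 112.x row removes anyone from a FAS.

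**Step 2: look for a rule on individual values.** SAP 6.3 covers safety measurements only. SAP 8.2.2 says missing titres are not imputed, but not that an erroneous one becomes missing. SAP 8.8 sets values below the limit of quantification to half that limit and does not mention invalid results. No rule was found.

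**Step 3: follow the Day 1 error into the Day 31 analyses.** Protocol 8.1.2.2 lists the Day 31/Day 1 GMR and the four-fold rise as secondary endpoints, and SAP 8.8 defines both against the earlier titre. Row 112.102 is blank under PPS Day 31. For these two endpoints the wrong baseline is therefore kept in both the FAS and the PPS for Day 31.

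**Step 4: scale.** The plan gives no figure to reproduce. The error rates, the fold error and the 15% rate below are assumptions.

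- GMT: if a fraction f of titres is wrong by a factor k in one direction, the group GMT is multiplied by k^f.
  - f = 0.02, k = 16: 16^0.02 = 1.057, a shift of 5.7%.
  - f = 0.05, k = 16: 16^0.05 = 1.149, a shift of about 15%.
  - One titre in 100 (the target enrolment per follow-on group), k = 16: 16^0.01 = 1.028, a shift of about 3%.
- GMR: the same errors in the Day 1 titres alone multiply the GMR by k^(−f), so f = 0.02 gives 1/1.057 = 0.946.
- Percentage ≥ LLOQ: with true rate p and a fraction f of the negatives falsely positive, the observed rate is p + f(1 − p). For p = 0.15 and f = 0.02 this is 0.15 + 0.02 × 0.85 = 0.167. In a group of 100, each false crossing moves the rate by 1 point.
- Between groups: equal f, k and direction give the same factor k^f in each group, which cancels in the GMT ratio. The shift f(1 − p) depends on p, so differences in percentages cancel less completely when the true rates differ.

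**The case against.** The strongest reply is that the table governs set membership, not values. A blank FAS cell says only that the subject stays in the set. The laboratory may simply not release an invalid result; it would then be missing, and if all eight were missing the 110.d codes would remove the subject from the relevant FAS. The word *evaluable* could be read the same way. The documents do not exclude this route, but they do not state it either. The *at least one result* condition would still admit a subject with one bad assay among eight.

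Second, a PPS analysis is always run, so an influential Day 1 error would appear as a FAS/PPS difference for the primary objective. That is true, but the PPS also drops subjects for unrelated deviations and so cannot isolate laboratory error. Nor does it help the Day 31 GMR and four-fold rise (Step 3).

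Third, code 112 is broader than confirmed error. It covers laboratory-manual deviations and, under section 6.1, incoherence and abnormal serology evolution. This stands. A reader might infer that everything coded 112 should leave the FAS; the documents do not support that. Removing titres because they look unusual, after results are seen in an open-label study, could itself bias the comparison.

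Two further inferences go too far. One is that an error in one assay necessarily costs the subject the other seven in the PPS: section 6.1 allows exclusion of part of a subject's data. The other is that the table dictates all programming: section 6.2 says only that the deviation listings are built from it, while the Exclusion Memo and the program specifications are separate documents not available here.

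Finally, testing is blind to arm and visit (Protocol 7.3), so there is no stated reason for errors to differ by arm. The study has no hypotheses or success criteria, so no decision threshold is at stake. Both points limit the consequence.

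**Conclusion.** The point holds for results confirmed as laboratory errors. As written, such values stay in the FAS, and a Day 1 error also stays as baseline in the Day 31 PPS. This rests on the cells of the section 7.7 table and on the absence of any value-level rule for titres in the SAP. It assumes that no rule in the unseen specifications or laboratory procedures already removes these results.

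The size cannot be stated. The 5.7% shift needs 2% of titres wrong 16-fold in one direction, and neither figure comes from the documents. A reader might infer that the reported group comparisons will be biased by that much; the documents do not support this, because errors at equal rates across groups would largely cancel in GMT ratios. The estimates most exposed are single-group GMTs, percentages and GMRs. The change is worth making before analysis because the gap affects the main set and is cheap to close.

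**What to change.** Split code 112 in SAP sections 6.1 and 7.7, using one description in both places.

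- **112a, documented invalid result.** The decision rests on laboratory QC records and is made without knowledge of arm and visit. The result is set to missing in all FAS and PPS sets, including as baseline for GMR and four-fold rise. The exclusion covers the affected strain and visit, or all results of the sample when the fault affects the whole sample. The subject's other valid results are kept.
- **112b, incoherence or abnormal serology evolution without a documented laboratory error.** The result stays in the FAS and is handled in the PPS only.

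A laboratory-manual deviation falls under 112a only if the QC record shows that the result is invalid. In SAP 7.3, add a sentence saying that a sample is evaluable for an assay only if the result is not coded 112a. A subject with an invalid Day 1 result then stays in the Day 31 sets for titres and percentages but drops out of the Day 31/Day 1 GMR and four-fold rise for that strain. This matches code 110.100, which leaves the Day 31 columns blank. List the 112a results and report their number by group, visit and strain.

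The cost is an edit to four table rows, the split definition, one sentence in 7.3 and result-level flags in the analysis data. The downside is a few fewer results in the FAS. No imputation is needed, in line with SAP 8.2.2.
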